#### Overview of Cost/Health Care Utilization Data.

Costs to be collected for the trial	From electric medical record	From patient report
Antidepressant cost, therapy cost, other mental health visits	Х	X
Depression-free days		X
Primary care visits, ED/urgent care, other medical visits, diagnostic services, inpatient services other outpatient services	Х	
Days able to work/impact on work and leisure productivity		X

We will generate cost data using a combination of EMR extraction and patient surveys as detailed in the table above. We will calculate the cost of all possible depression care used (antidepressant cost and therapy cost. We will also collect data on all non-study delivery of depression treatment utilization from patient report and EMR. To derive other healthcare costs, we will use the EMR to collect data on all episodes of non-depression related healthcare utilization during the 18-month trial period: outpatient visits, ED/urgent care, as well as all in-patient care and any diagnostic tests or services. Average Medicare reimbursement rates according to diagnosis-related groups will be applied to inpatient visits to estimate hospitalization costs, and the Medicare fee schedule will be applied to outpatient and ED resource use according to current

procedural terminology codes. Finally, to calculate costs and potential cost-offsets from a societal perspective, we will collect participant report data on time lost from work. Lost productivity is believed by many experts to be assessed in our measure of health-related QoL instrument, the SF12. However, a sensitivity analysis will be conducted to test this assumption.

# **Participant Timeline**

Table 1. Schedule of screening, baseline and follow-up forms

Form Name	Screening	Baseline	6 Months	12 Months	18 Months
Screening Questionnaire	X				
Subject Contact Information		Χ			
Subject Contact Information Update Form (if indicated)			Х	Х	Х
Demographics		Χ			
PHQ-8		Χ*			Х
CES-D10		Х	Х	Х	Х
SF-12		Χ	Χ	Χ	X
Health Service Use Questionnaire			Х	Х	Х
Symptoms Checklist		Χ	Χ	Χ	X
Lost Productivity Questionnaire		Χ	Χ	Χ	X
Unanticipated Event Report			۸	۸	٨
Quality Assurance Form**			Х	Х	X

\*Participants randomized to the No Depression Screen arm will NOT complete PHQ-8 at baseline

#### Sample Size

For the primary outcome in Aim 1, we will be making two primary comparisons: Difference in QALYs comparing AHA's Screen, Notify & Treat group vs. Screen & Notify and then separately to No Screen group. For choosing a sample size, we assumed a standard deviation for QALYs in the conservative control group (e.g., no depression screen) of 0.17. Additionally, based on a prior study of management of depression for patients with cancer, we assumed a net improvement in QALYs of 0.155 over 18 months of follow-up for individuals receiving the AHA's screen & treat intervention would be reasonable to expect. We assumed a 0.055 gain in QALYs for all participants not receiving treatment (i.e., those in the No Screen group, the Screen & Notify group and those without depression in the AHA's Screen, Notify & Treat group). An important consideration for this trial is that only 20% of patients randomized to the AHA's Screen, Notify & Treat group will meet criteria for depression and thus will receive the treatment part of intervention. Therefore, assuming an improvement in QALYs of 0.21 (0.055 background improvement + net improvement of 0.155) over the 18-month follow-up period for the 20% of participants with diagnosed depression and a 0.055 improvement in QALYs for the 80% of participants in this randomization group without depression, an overall gain in QALYs of 0.086 over the 18-month follow-up period can be anticipated in

\*\* For blinded coordinator only

\*Only completed if necessary

this randomization group (0.21 \* 0.2 + 0.055 \*0.8 = 0.086). Thus, we anticipate a relative difference in QALYs of 0.031 (0.086 change in the AHA's screen & treat group minus 0.055 in the no screen group). We will have 80% statistical power to detect this difference of 0.031 with a sample size of n=475 participants in each group. We chose to determine sample size based on a pairwise comparison at 80% power in the two-step procedure, as a conservative approach relative to powering based on the F-test (See Statistical Analysis section, below, for further details). Specifically, under the scenario where one group has higher QALY than the other two by an effect size 0.18, the F-test will yield 84% power. Adding in 5% loss to follow-up, we selected an overall sample size of n=500 in each randomization group for an overall sample size of n=1500. Power analyses are typically based on the primary clinical outcome. We selected the QALY as our primary outcome and did not have specific economic hypotheses that required statistically tests. Therefore, we chose to follow this tradition, and do not present power calculations for our incremental cost-effectiveness ratios.

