# **Hypothesis 1:**

Those randomized to AHA's Depression Screen, Notify & Treat intervention group will gain significantly more quality-adjusted life years across 18 months when compared to No Depression Screen control group, and also when compared to the Depression Screen & Notify control group.

We will compare outcomes for participants randomized to each of the three groups. Change in QALYs from baseline through 18 months post-randomization will serve as the primary outcome for this trial. First, quality of life utilities will be calculated using participants' scores on the SF-12 at each visit (baseline [pre-randomization] and 6, 12,

and 18 months post-randomization). All participants who complete the SF-12 will be classified according to the SF-6D. The SF-6D describes 18,000 health states. The average profile for each randomized group will be calculated. A multiple regression formula that applies weights will be used to assign quality of life utilities for each participant. Next, QALYs will be derived by multiplying the SF-6D derived quality of life utilities by 0.5 years for each 6 month-period, assuming linearity for changes in utility within each period. Any mortality events will be assigned zero QALYs from that point to the end of follow-up. With these scores calculated, we will calculate the average QALY gained (or lost) in each randomized group compared to assuming the utility calculated at baseline remained constant across 18-months.

The goal of the primary analysis is to identify whether there is difference in QALYs among the three groups. We plan to perform a two-step gate-keeping test procedure: We will first perform an F-test using ANOVA, and then proceed to do all three pairwise comparisons using two-sided t-test at 5% nominal significance *only if* the F-test has a p-value less than 0.05. With three randomization groups and three pairwise comparisons, this two-step procedure has been shown to preserve the familywise error rate in the strong sense, that is, a false positive comparison will occur at most with 5% probability under all possible scenarios.  This method is also generally more powerful than Bonferroni's adjustments.

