5.3 Primary Efficacy Analysis

Change in QALYs from baseline through 18 months post-randomization will serve as the primary outcome for this trial. QALYs were chosen as the primary outcome to facilitate comparisons of the effect of depression screening with other preventive interventions as well as to facilitate cost-effectiveness analyses and policy decisions. As QALYs do not directly assess depression, this outcome measure also minimized possible patient reporting bias as a result of lack of participant blinding or masking to condition. The goal of the primary analysis is to identify whether there is difference in the change in QALYs among the three groups. QALYs describe the duration of illness per years of survival, adjusted for quality of life experienced during that survival. One year in perfect health is equivalent to 1 QALY. All patients will complete a standardized measure of quality of life using the Short Form-12 Health Survey, Version 2™ (SF-12) at baseline, and again at 6-months, 12-months, and 18-months. 1 QALYs will be estimated from the SF-12 using the Short Form 6 Duration (SF6D) which converts data from 7 items in the SF-12 assessing 6 domains (physical functioning, role limitations, social functioning, pain, mental health and vitality) to QALYs.2 Study patients who die during the study period will be assigned a utility score of 0 for assessments after the date of death. QALYs over 18 months will be calculated as the area-under-curve by interpolating linearly the scores at the four assessments (baseline, 6-month, 12-month, 18-month). There were no data obtained or available for these measures between assessments. Change in QALYs will then be obtained by subtracting the QALYs that would have occurred if there was no change in the baseline utility score from the actual QALYs that were measured across 18 months. The analysis will follow the principle of intention-to-treat and will be conducted on each imputed dataset with the point

estimate deriving from the average of 5 datasets and the pooled variance calculated using Rubin's formula.

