To determine the significance of differences, we will perform a two-step gate-keeping test procedure. This will involve first performing an F-test using ANOVA, and then proceeding to do all three pairwise comparisons using two-sided t-test at 5% nominal significance *only if* the F-test has a p-value less than 0.05. With three randomization groups and three pairwise comparisons, this two-step procedure can be shown to preserve the familywise error rate in the strong sense, that is, a false positive comparison will occur at most with 5% probability under all possible scenarios._{3,4} This method is also generally more powerful than Bonferroni's adjustments.

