5.4 Sample Size Determination

The sample size of the trial was determined based on an assumed standard deviation for QALYs of 0.17.5 Additionally, based on a general health-related quality of life outcome in a prior study of management of depression for patients with cancer, we assumed a net improvement in QALYs of 0.155 over 18 months of follow-up for depressed individuals who receive depression treatment in the Screen, Notify and Treat group.6 We assumed a 0.055 gain in QALYs for all patients not directly linked to depression treatment (i.e., those in the No Screen group, the Screen & Notify group and those without elevated depressive symptoms in the Screen, Notify, and Treat group). An important consideration for this trial is that only 20% of patients randomized to the Screen. Notify and Treat group were expected to meet criteria for elevated depressive symptoms and thus, to receive depression treatment. Therefore, assuming an increase in QALYs of 0.21 (0.055 background improvement + net improvement of 0.155) over the 18-month follow-up period for the 20% of patients diagnosed and treated for depression in the Screen, Notify, and Treat group and a 0.055 improvement in QALYs for the 80% of patients in this randomization group without depression, an overall gain in QALYs of 0.086 over the 18 month follow-up period was anticipated in this randomization group (0.21 * 0.2 + 0.055 * 0.8 = 0.086). Thus, we anticipated a difference in QALYs of 0.031 (0.086 change in the Screen. Notify, and Treat group minus 0.055 in the No Screen group or Screen and Notify Group), leading to an expected effect size of 0.18 (= 0.031/0.17). With this effect size, we determined the sample size per group to be 475, which would yield 80% power for a two-sided t-test at 5% level. We chose to determine sample size based on a pairwise comparison at 80% power in the two-step procedure (described above), as a conservative approach relative to powering based on the F-test. Specifically, under the scenario where one group has higher QALY than the other two by an effect size 0.18, the F-test will yield 84% power. Adding in 5% loss to follow-up, we selected an overall sample size of n=500 in each randomization group for an overall sample size of n=1500.

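### The 80% power attributed to the two-step procedure belongs to a single t-test without the F-gate; through the gate, one named comparison has about 76% at 475 per arm and 78% at 500

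*Protocol*

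**What the plan says.** The protocol's Sample Size section names two primary comparisons, Screen, Notify & Treat against each control. It gives 475 per group with this statement: "We will have 80% statistical power to detect this difference of 0.031". It then explains the choice: "We chose to determine sample size based on a pairwise comparison at 80% power in the two-step procedure". It calls this conservative compared with powering on the F-test, gives 84% for the F-test, and points the reader onward: "See Statistical Analysis section, below, for further details".

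SAP 5.4 also bases the size on "a pairwise comparison at 80% power in the two-step procedure (described above". Its preceding sentence describes 475 per group as the number "which would yield 80% power for a two-sided t-test at 5% level". The protocol has no equivalent of that sentence.

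The procedure that both refer to is defined under Hypothesis 1 in the protocol's Statistical Methods and in SAP 5.3. An ANOVA F-test comes first. The pairwise tests follow only if "the F-test has a p-value less than 0.05", and the SAP describes the second step as "then proceeding to do all three pairwise comparisons using two-sided t-test at 5% nominal significance".

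**The concern.** Under the two-step rule, a named comparison is declared significant only if the F-test and that t-test are both significant. The power of this joint event cannot exceed the power of either test, and it is lower whenever a significant t-test can occur with a non-significant F-test. That happens when the third arm's mean falls between the other two. An 80% that belongs to the t-test alone therefore cannot also be the power of that comparison in the two-step procedure.

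The two-step rule decides both primary comparisons. If one is not significant, readers will use the stated power to judge what the trial could have detected. With only 80% and 84% in front of them, they would take at least 80% for a named comparison, when the true figure is below both.

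**Working it through.** **Inputs, all from the documents**
- Difference in QALYs, Screen, Notify & Treat against either control: 0.031 (0.086 − 0.055).
- SD: 0.17. Standardised effect: d = 0.031/0.17 = 0.1824, printed in SAP 5.4 as 0.18.
- The two controls are equal, both at 0.055. Allocation is 1:1:1.
- Two-sided 5% t-tests, behind an F-test at 5%.
- 475 analysed per arm. 500 enrolled per arm after the plan's 5% loss (475/0.95 = 500).

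**Step 1: reproduce the stated 80%.** For one ungated t-test the noncentrality is d·√(n/2), on 2n − 2 degrees of freedom. At n = 475 this is 0.1824 × √237.5 = 2.81, and the power is 80.2%. At n = 500 it is 2.88, and the power is 82.1%. The test first reaches 80% at 474 per arm. The stated 80% at 475 is therefore the ungated t-test.

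**Step 2: reproduce the stated 84%.** With one mean higher by d and the other two equal, the noncentral F has λ = n·(2/3)·d² on 2 and 3n − 3 degrees of freedom. At 475, λ = 475 × (2/3) × 0.03325 = 10.53, and the power is 83.5%. At 500 it is 85.5%. The F-test needs 436 per arm for 80%, so sizing on the pairwise t-test is indeed conservative relative to sizing on the F-test.

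**Step 3: why the gate costs power.** Take a given observed difference in the named pair. With equal arms and a common variance estimate, F is smallest when the third mean lies midway between the two, and it then equals t²/2. The 5% critical value of F on 2 and 1,422 degrees of freedom is 3.00. A t-test is therefore certain to pass the gate only if |t| exceeds √(2 × 3.00) = 2.45. Values between 1.96 and 2.45 are significant on the t-test but can be stopped by the gate.

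**Step 4: power of the planned rule.** The rule was simulated with normal data and equal variances, 4 million trials per case. A success is F significant at 5%, the named t-test significant at 5%, and the difference in favour of Screen, Notify & Treat.

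| Per arm | d | t-test alone | F-test | One named comparison through the gate |
|---|---|---|---|---|
| 475 | 0.1824 | 80.2% | 83.5% | 75.9% |
| 500 | 0.1824 | 82.1% | 85.5% | 78.3% |
| 475 | 0.18 | 79.1% | 82.5% | 74.7% |

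At 475 the gate blocks an otherwise significant t-test in 4.3% of trials, which is the whole gap (80.2 − 75.9 = 4.3). At 500 it blocks 3.9%. Using the pooled three-arm variance in the t-test changes the gated figures by less than 0.1 point.

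**Step 5: size for 80% through the gate.** Gated power is 79.9% at 519 and 80.0% at 520 analysed per arm. Allowing for 5% loss, 520/0.95 = 547.4, or 548 enrolled per arm.

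**Related figure.** Hypothesis 1 asks for superiority over both controls. Power to win both is 68.3% through the gate at 475 (71.1% at 500) and 68.9% at 475 without it. That loss comes almost entirely from requiring two wins.

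**The case against.** The strongest reply is that nothing was miscalculated: the 80%, 475, 84% and 500 all reproduce. On this view the disputed phrase only says which step of the procedure set the sample size, the pairwise step rather than the F-test, and SAP 5.4 labels the 80% as a two-sided t-test in the sentence before. The wording allows that reading. But the protocol carries no such label, and the SAP's label confirms that the 80% ignores the gate. On either reading, neither document gives the power of a pairwise test that must first pass the F-test.

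A second reply is that SAP 5.3 sets the primary goal as to "identify whether there is difference in the change in QALYs among the three groups". The F-test serves that goal with 84%, and power to find at least one of the two true differences through the gate is 83.5%. Both figures are right, and that goal is met. But neither document claims power for at least one difference, SAP 5.4 ties the 80% to a single t-test, and the protocol names two separate primary comparisons.

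A third reply is that the gap is small beside the uncertainty in the inputs. That is true: merely rounding d to 0.18 moves the F-test to 82.5%. But uncertainty in the SD or the effect moves the gated and ungated figures together. The gap between them is a property of the rule. The point remains modest, and it calls for a correction of text only.

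**Conclusion.** The concern holds. The 80% is the power of one t-test taken alone, and both documents attribute it to a procedure that delivers less. For one named comparison through the gate, power is 75.9% with 475 analysed per arm, the number left by the plan's own 5% loss. It is 78.3% if all 500 contribute full information. With multiple imputation the effective number lies between these, so about 76% to 78% is the fair range. The chance of missing a true difference in a named comparison is about 24% at 475, not 20%.

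This assumes normal data with equal variances, the stated difference and SD, and equal controls, as the plan does. If Screen & Notify instead lay midway between the other two arms, gated power for Screen, Notify & Treat against No Screen would be about 70% at 475.

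The stated F-test power, the description of the pairwise size as conservative relative to the F-test, and the type I error of the procedure are not in question here.

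**What to change.** Change the text only, in the protocol's Sample Size section and SAP 5.4.

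1. Replace the sentence that ties the 80% to the two-step procedure with wording such as: *With 475 analysed per group, a single two-sided t-test at the 5% level, taken alone, has 80% power. Under the two-step procedure, where that test is done only after a significant F-test, power for one named comparison is about 76% (about 78% if all 500 per group are analysed). The F-test itself has 84%.*
2. Keep the statement that the pairwise size is conservative relative to powering on the F-test.
3. Optionally, because Hypothesis 1 requires superiority over both controls, add that power to win both is about 68% at 475 per group and that this comes from requiring both, not from the gate.

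The cost is a few sentences in each document and a slightly less favourable stated power. Sample size, data collection and the test procedure stay as they are.

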#### Recruitment

The four participating health care organizations have different methods of recruiting however, they will all utilize an electronic medical record (EMR) algorithm to identify medically eligible patients. At the EMR eligibility stage, electronic medical records will be screened for documented ACS, age, language preference, and all other medical and psychiatric eligibility criteria. Patients identified as potentially eligible through this process may be contacted by mail, postcard, or email and offered either an email address or telephone number to contact if interested in study participation. This initial contact may include a study brochure, letter on behalf of their primary care provider, and/or a copy of the Informed Consent Form. Patients who express interest may either be screened and introduced to the consenting process over the phone, or scheduled for an in-person study screening and consent visit depending upon local practices and IRB approval.

In general, those who do respond by email or phone within approximately 2 weeks after the date of initial contact will be telephoned by the recruitment staff. We will carefully document who did not complete screening, who was ineligible (and for what reason) and who refused. Patients who consented and are eligible after screening will then be randomized during the either the initial telephone call, a follow-up phone call or at an inperson visit. Participants who are randomized to Depression Screen & Notify arm will complete a PHQ-8 assessment, and those with clinically significant scores (≥ 10) will have a letter sent to their PCP and/or cardiologist. Participants who are randomized to the AHA Depression Screen, Notify & Treat arm will also complete a PHQ-8 assessment, and those with clinically significant scores (≥ 10) will be offered the option of receiving treatment for their depressive symptoms. Participants will be presented with the option of receiving medication therapy (sertraline), Cognitive Behavioral Therapy (delivered via phone), a combination of both therapies or neither therapy. Depending on their treatment choice, they will be scheduled for their initial treatment visit, ideally within two weeks of randomization, depending on their treatment choice. Those with clinically significant scores (≥ 10) in the Depression Screen, Notify, & Treat group will also have a letter sent to their PCP and/or cardiologist in the same manner as patients in the Screen & Notify group. Those randomized to the No Depression Screen group will not receive the depression screen (PHQ-8) at baseline.

# **Assignment of Interventions**

#### Sequence generation

Participants will be randomly assigned to one of three groups: No Depression Screen, Depression Screen and Notify, or AHA Depression Screen, Notify and Treat. The randomization algorithm will be embedded in the web-based tracking system, using randomly assigned block sizes of 3, 6 and 9.

#### **Concealment Mechanism**

Participants will be randomized using the web-based tracking system. "User-roles" are assigned to study personnel, and the randomization tool is only available to unblinded coordinators at each site. Concealment will be ensured as the randomization algorithm will run in the backend, and only the randomization assignment will be visible to the unblinded coordinator after all necessary information about the participant has been entered.

